10.3 Nivolumab

Nivolumab (ONO-4538, MDX-1106, BMS-936558-01 or BMS-936558) is an anti-PD-1, anti-programmed cell death-1 monoclonal antibody.

10.3.1 Supplier/How Supplied

Bristol-Meyers Squibb will supply nivolumab at no charge to subjects participating in this clinical trial.

The site investigator shall take responsibility for and shall take all steps to maintain appropriate records and ensure appropriate supply, storage, handling, distribution, and usage of investigational product in accordance with the protocol and any applicable laws and regulations.

A copy of the drug destruction certificate should be maintained for provision to BMS at the end of the study

10.3.2 Product Description and Dosage Form

Nivolumab Injection, 100mg/10 mL (10mg/mL) is a clear to opalescent, colorless to pale yellow liquid, which may contain light (few) particulates. The drug product is a sterile, non-pyrogenic, single-use, isotonic aqueous solution formulated at 10 mg/mL in sodium citrate, sodium chloride, mannitol, diethylenetriaminepentaacetic acid (pentetic acid), and polysorbate 80 (TweenTM 80), pH 6.0 and includes an overfill to account for vial, needle, and syringe holdup. It is supplied in 10-cc Type I flint glass vials, stoppered with butyl rubber stoppers and sealed with aluminum seals. The only difference between the two drug product presentations is the vial fill volume.

10.3.3 Storage and Stability

Clinical supplies must be stored in a secure, limited-access location under the storage conditions specified on the label. Store nivolumab under refrigeration at 2°C to 8°C (36°F to 46°F). Protect nivolumab from light by storing in the original package until time of use. Do not freeze or shake. For

additional details on prepared drug storage and use time of nivolumab under room temperature/light and refrigeration, please refer to the BMS-936558 (nivolumab) Investigator Brochure section for “Recommended Storage and Use Conditions.”

Undiluted Nivolumab Injection and Diluted Nivolumab Injection in the IV Container

The administration of nivolumab infusion must be completed within 24 hours of preparation. If not used immediately, the infusion solution may be stored under refrigeration conditions (2°C to 8°C, 36°F to 46°F) for up to 24 hours, and a maximum of 8 hours of the total 24 hours can be at room temperature (20°C to 25°C, 68°F to 77°F) and room light. The maximum 8-hour period under room temperature and room light conditions includes the product administration period.

10.3.4 Dispensing

Nivolumab must be dispensed only from official study sites and to eligible subjects under the supervision of the site investigator. Nivolumab should be stored in a secure area according to local regulations. It is the responsibility of the site investigator to ensure that study drug is only dispensed to subjects.

10.3.5 Administration

Nivolumab is to be administered as an IV infusion through a 0.2-micron to 1.2-micron pore size, low-protein binding (polyethersulfone membrane) in-line filter at the protocol-specified doses and infusion times. It is not to be administered as an IV push or bolus injection. Nivolumab injection can be infused undiluted (10 mg/mL) or diluted with 0.9% Sodium Chloride Injection, USP or 5% Dextrose Injection, USP to protein concentrations as low as 0.35 mg/mL. During drug product preparation and handling, vigorous mixing or shaking is to be avoided. Care must be taken to assure sterility of the prepared solution as the product does not contain any antimicrobial preservative or bacteriostatic agent. No incompatibilities between nivolumab and polyvinyl chloride (PVC) and non-PVC/non-DEHP (di(2-ethylhexyl)phthalate) containers/IV components or glass bottles have been observed.

10.3.6 Adverse Events

Please refer to the nivolumab Investigator’s Brochure for a complete list of adverse events.

Potential safety concerns and recommended management guidelines regarding pulmonary toxicities, GI toxicities, hepatotoxicities, endocrinopathies, dermatologic toxicities, and other toxicities of concern are summarized below. Management algorithms are found in Appendix 2.

The overall safety experience with nivolumab is based on experience in approximately 12,300 subjects as either monotherapy or in combination with other therapeutics. In general, for monotherapy, the safety profile is similar across tumor types. The only exception is pulmonary inflammation AEs, which may be numerically greater in subjects with NSCLC, possibly because in some cases, it can be difficult to distinguish between nivolumab-related and unrelated causes of pulmonary symptoms and radiographic changes. The most frequently reported treatment-related AE is fatigue, which is almost always of low grade.

Most related AEs are thought to be due to the effects of inflammatory cells on specific tissues. A variety of preferred terms (PTs) have been used to describe similar kinds of organ-related AEs, with the result being that AE frequency tables organized by PTs can lead to underestimation of the frequency of similar kinds of organ-related AEs. Select AE categories group together the most common and impactful PTs by

organ category. These categories include the following: pulmonary, GI, hepatic, skin, endocrine, hypersensitivity/infusion reaction, and renal AEs.

Pulmonary Adverse Events

Pulmonary AEs have been observed following treatment with nivolumab. The frequency of pulmonary AEs may be greater with nivolumab combination therapies than with nivolumab monotherapy. The majority of cases reported were Grade 1 or 2, and subjects presented with either asymptomatic radiographic changes (e.g., focal ground glass opacities and patchy infiltrates) or with symptoms of dyspnea, cough, or fever. Subjects with reported Grade 3 or 4 pulmonary AEs were noted to have more severe symptoms, more extensive radiographic findings, and hypoxia. Pulmonary AEs have been reported in subjects with a variety of tumor types; however, there have been numerically more cases in subjects with NSCLC. It is not clear whether the underlying NSCLC is a distinct risk factor, or if subjects with NSCLC are more likely to develop radiographic changes and symptoms for which it is difficult to distinguish between nivolumab-related and unrelated causes. At this time, no other underlying risk factor, including prior radiotherapy, presence of lung metastases, or underlying pulmonary medical history, has yet to be identified.

Gastrointestinal Adverse Events

Gastrointestinal AEs have been observed following treatment with nivolumab. Most cases of diarrhea were of low grade (Grade 1-2). Colitis occurred less frequently than diarrhea. High-grade cases of diarrhea and colitis were managed with corticosteroids and, in all cases, the events resolved.

Diverticular Perforation

The prevalence of diverticulosis in the general population is common and increases with age from 10% under 40 years of age to approximately 50% over 60 years of age. Approximately 10% to 25% of subjects with diverticulosis develop diverticulitis. Perforation occurs in 50% to 70% of instances of complicated diverticulitis [36, 37]. Corticosteroids, non-steroidal anti-inflammatory drugs (NSAIDs), and opioid analgesics are known risk factors for diverticular perforation [38]. Given the high prevalence of diverticulosis and diverticulitis in the general population, it is expected that some nivolumab-treated subjects will have these conditions concurrently with their malignancy. Cases of diverticular perforation while on concomitant corticosteroids (6 cases) or NSAID (1 case) were observed in nivolumab program. While there is insufficient evidence to suggest that diverticulosis or diverticulitis is a predisposing factor for GI perforation following nivolumab administration, clinical caution should be exercised, as appropriate, for subjects on concomitant medications of corticosteroids, NSAID, or opioid analgesics. In addition, be vigilant for signs and symptoms of potential perforation, especially in subjects with known diverticular disease.

Hepatic Adverse Events

Hepatic AEs, including elevated liver function tests (LFTs) and, infrequently, drug-induced liver injury (DILI) have been observed following treatment with nivolumab and nivolumab in combination with ipilimumab. Most cases were of low or moderate grade. Higher-grade hepatic AEs, including DILI, were managed with corticosteroids (with or without mycophenolate mofetil) and, in almost all cases, the events resolved.

Endocrinopathies

Endocrinopathies have been observed following treatment with nivolumab. Most cases were of low or moderate grade. The events have typically been identified through either routine periodic monitoring of specific laboratories (e.g., TSH) or as part of a work-up for associated symptoms (e.g., fatigue). Events may occur within weeks of beginning treatment, but also have been noted to occur after many months (while still on treatment). More than 1 endocrine organ may be involved (e.g., hypophysitis [pituitary inflammation] may need to be evaluated at the time adrenal insufficiency or thyroid disorder is suspected). Moderate- to high-grade cases were managed with hormone replacement therapy and, in some cases, with the addition of corticosteroids. In some cases, nivolumab treatment was held until adequate hormone replacement was provided.

Skin Adverse Events

Rash and pruritus were the most common skin AEs observed following treatment with nivolumab. The rash was typically focal with a maculopapular appearance occurring on the trunk, back, or extremities. Most cases have been of low or moderate grade. In some cases, rash and pruritus resolved without intervention. Topical corticosteroids have been used for some cases of rash. Anti-histamines have been used for some cases of pruritus. More severe cases responded to systemic corticosteroids.

Renal Adverse Events

Elevated creatinine and biopsy-confirmed tubulointerstitial nephritis and allergic nephritis have been infrequently observed following treatment with nivolumab. The frequency of renal AEs may be greater with nivolumab combination therapies than with nivolumab monotherapy. Most cases were Grade 2 or 3 and based on creatinine elevation. Subjects with a history of renal cell carcinoma or prior nephrectomy did not appear to be at higher risk. Events were managed with corticosteroids and, in all cases, renal function partially or fully improved.

Neurologic Adverse Events

Neurologic AEs have been uncommonly observed following treatment with nivolumab. The frequency of neurologic AEs may be greater with nivolumab + ipilimumab combination therapies than with nivolumab monotherapy or other nivolumab combinations. Neurologic AEs can manifest as central abnormalities (e.g., aseptic meningitis, encephalopathy, or encephalitis) or peripheral sensory/motor neuropathies (e.g., Guillain-Barre Syndrome, myasthenia gravis complicated with sepsis and fatality). The onset has been observed as early as after a single treatment with the nivolumab + ipilimumab combination.

Infusion Reactions

Infusion reactions, including high-grade hypersensitivity reactions, following administration of nivolumab are uncommon. Investigators are advised to monitor for fever, chills, shakes, itching, rash, hypertension or hypotension, or difficulty in breathing during and immediately after administration of nivolumab.

Lipase/Amylase Elevations

Asymptomatic elevations in lipase and amylase have been reported. In monotherapy studies, lipase and amylase levels were not systematically monitored, so an estimate of the frequency of asymptomatic lipase/amylase elevations is unknown. In studies evaluating the safety of the nivolumab + ipilimumab combination in multiple tumor types, lipase and amylase levels were systematically monitored, and

elevations in any grade of lipase/amylase were consistently noted in approximately 10% to 30% of subjects. Very few subjects reported associated symptoms (e.g., abdominal pain) or radiographic findings (e.g., stranding) consistent with pancreatitis. Thus, there does not seem to be clinical significance to the elevated laboratory values.

Uveitis and Visual Complaints

Immune therapies have been uncommonly associated with visual complaints. Inflammation of components within the eye (e.g., uveitis) is an uncommon, but clinically important, event. Uveitis may occur more frequently with nivolumab + ipilimumab combination therapy than with nivolumab monotherapy or nivolumab in combination with other therapies. An ophthalmologist should evaluate visual complaints with examination of the conjunctiva, anterior and posterior chambers, and retina. Topical corticosteroids may be used to manage low-grade events. Low-grade events that do not resolve and high-grade events should be managed with systemic corticosteroids. Consultation with the sponsor-investigator should be sought for all cases of ocular inflammatory events. Complaints of double vision should also prompt medical evaluation. In addition to ocular inflammatory events, a work-up should also consider pituitary inflammation as a cause.

Other Immune-mediated Adverse Events

For suspected immune-related adverse reactions, adequate evaluation should be performed to confirm etiology or exclude other causes. Based on the severity of the adverse reaction, nivolumab or nivolumab in combination with ipilimumab should be withheld and corticosteroids administered. Upon improvement, nivolumab or nivolumab in combination with ipilimumab may be resumed after corticosteroid taper. Nivolumab or nivolumab in combination with ipilimumab must be permanently discontinued for any severe immune-related adverse reaction that recurs and for any life-threatening immune-related adverse reaction.

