6.1.3 Nivolumab

There are no dose reductions for nivolumab. For toxicity as outlined in this protocol, study therapy should be delayed until the AE improves to the stated level or should be discontinued permanently depending on severity (see table below). If a dose of nivolumab is held for toxicity and cannot be resumed within 48 hours, the dose will not be made up, and the subject will continue to follow the standard dosing schedule. If the dose of nivolumab is held for toxicity and can be resumed within 48 hours, the dose will be given, and the subject will continue to follow the standard dosing schedule (i.e., the next dose will be given on time).

Dose delay guidelines for nivolumab related adverse events

Recommendations for nivolumab modifications are below. When nivolumab is administered with ipilimumab, if nivolumab is held then ipilimumab should also be held.

Adverse Reaction	Severity*	Dose Modification
Colitis	Grade 2 diarrhea or colitis	Withhold dose ^a
	Grade 3 diarrhea or colitis	Withhold dose ^a when administered as a single agent
	Grade 4 diarrhea or colitis	Permanently discontinue when administered with ipilimumab
Pneumonitis	Grade 2 pneumonitis	Withhold dose ^a
	Grade 3 or 4 pneumonitis	Permanently discontinue
Hepatitis/non-HCC ^b	Aspartate aminotransferase (AST) or alanine aminotransferase (ALT) more than 3 and up to 5 times the upper limit of normal (ULN) or total bilirubin more than 1.5 and up to 3 times the ULN	Withhold dose ^a
	AST or ALT more than 5 times the ULN or total bilirubin more than 3 times the ULN	Permanently discontinue
Hepatitis/ HCC ^b	
 If AST/ALT is within normal limits at baseline and increases to more than 3 and up to 5 times the ULN If AST/ALT is more than 1 and up to 3 times ULN at baseline and increases to more than 5 and up to 10 times the ULN If AST/ALT is more than 3 and up to 5 times ULN at baseline and increases to more than 8 and up to 10 times the ULN 	Withhold dose ^c
	If AST or ALT increases to more than 10 times the ULN or total bilirubin increases to more than 3 times the ULN	Permanently discontinue
Hypophysitis	Grade 2 or 3 hypophysitis	Withhold dose ^a
	Grade 4 hypophysitis	Permanently discontinue
Adrenal Insufficiency	Grade 2 adrenal insufficiency	Withhold dose ^a
	Grade 3 or 4 adrenal insufficiency	Permanently discontinue

Adverse Reaction	Severity*	Dose Modification
Type 1 Diabetes Mellitus	Grade 3 hyperglycemia	Withhold dose ^a

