	Grade 4 hyperglycemia	Permanently discontinue
Nephritis and Renal Dysfunction	Serum creatinine more than 1.5 and up to 6 times the ULN	Withhold dose ^a
	Serum creatinine more than 6 times the ULN	Permanently discontinue
Skin	Grade 3 rash or suspected Stevens-Johnson syndrome (SJS) or toxic epidermal necrolysis (TEN)	Withhold dose ^a
	Grade 4 rash or confirmed SJS or TEN	Permanently discontinue
Encephalitis	New-onset moderate or severe neurologic signs or symptoms	Withhold dose ^a
	Immune-mediated encephalitis	Permanently discontinue
Other	Other Grade 3 adverse reaction	
	First occurrence	Withhold dose ^a
	Recurrence of same Grade 3 adverse reactions	Permanently discontinue
	Life-threatening or Grade 4 adverse reaction	Permanently discontinue
	Grade 3 myocarditis	Permanently discontinue
	Requirement for 10 mg per day or greater prednisone or equivalent for more than 12 weeks	Permanently discontinue
	Persistent Grade 2 or 3 adverse reactions lasting 12 weeks or longer	Permanently discontinue

* Toxicity was graded per National Cancer Institute Common Terminology Criteria for Adverse Events. Version 4.0 (NCI CTCAE v4).

^a Resume treatment when adverse reaction improves to Grade 0 or 1.

^b HCC: hepatocellular carcinoma.

^c Resume treatment when AST/ALT returns to baseline.

Dose delay guidelines for ipilimumab related adverse events

Recommendations for nivolumab modifications are below. When nivolumab is administered with ipilimumab, if nivolumab is held then ipilimumab should also be held.

Mild to moderate adverse reactions	Action
Gastrointestinal: Moderate diarrhoea or colitis that either is not controlled with medical management or that persists (5-7 days) or recurs	1. Withhold dose until an adverse reaction resolves to Grade 1 or Grade 0 (or returns to baseline). 2. If resolution occurs, resume therapy. ^d 3. If resolution has not occurred, continue to withhold doses until resolution then resume treatment. ^d 4. Discontinue YERVOY if resolution to Grade 1 or Grade 0 or return to baseline does not occur.
Hepatic: Moderate elevations in transaminase (AST or ALT > 5 to ≤ 8 x ULN) or total bilirubin (> 3 to ≤ 5 x ULN) levels	
Skin: Moderate to severe (Grade 3) ^b skin rash or widespread/intense pruritus regardless of etiology	
Endocrine: Severe adverse reactions in the endocrine glands, such as hypophysitis and thyroiditis that are not adequately controlled with hormone replacement therapy or high-dose immunosuppressive therapy	

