6.2 Protocol Therapy Discontinuation

In addition to discontinuation from therapy related to toxicities as outlined in section 6.1, a subject will also be discontinued from protocol therapy and followed up per protocol under the circumstances outlined below. The reason for discontinuation of protocol therapy will be documented on the eCRF.

- Documented disease progression per RECIST 1.1.
- The treating physician thinks a change of therapy would be in the best interest of the subject
- The subject requests to discontinue protocol therapy, whether due to unacceptable toxicity or for other reasons
 - If a subject decides to prematurely discontinue protocol therapy (“refuses treatment”), the subject should be asked if he or she may still be contacted for further scheduled study assessments. The outcome of that discussion should be documented in both the medical records and in the eCRF.
- A female subject becomes pregnant

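### Section 10.3.6 requires a permanent stop when a severe immune-related reaction recurs, but the Grade 3 rash row of the 6.1.3 nivolumab table says withhold and resume, with no recurrence stop

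*Combined protocol and SAP*

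**What the plan says.** Section 10.3.6, in its closing paragraph on other immune-mediated events, sets a mandatory rule for nivolumab and for nivolumab with ipilimumab: treatment "must be permanently discontinued for any severe immune-related adverse reaction that recurs and for any life-threatening immune-related adverse reaction".

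Section 6.2 treats section 6.1 as the place where stopping for toxicity is set out: "In addition to discontinuation from therapy related to toxicities as outlined in section 6.1". Section 6.1.3 in turn refers sites to its tables. In the nivolumab table the skin row for withholding reads "Grade 3 rash or suspected Stevens-Johnson syndrome (SJS) or toxic epidermal necrolysis (TEN" (closing bracket not included). Its footnote reads "Resume treatment when adverse reaction improves to Grade 0 or 1". Grade 4 rash and confirmed SJS or TEN are permanent stops.

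The same table does contain a recurrence stop. It sits in the last block, under the label "Other Grade 3 adverse reaction": a first occurrence is withheld and a recurrence of the same Grade 3 reaction is a permanent stop.

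**The concern.** The strict rule is in the drug-information chapter, while the text that sites use to decide on dosing is the 6.1.3 table. For a second Grade 3 rash that has again settled to Grade 0 or 1, the row read literally leads to resumption, whereas 10.3.6 leads to permanent discontinuation. At stake is re-exposure of a patient whom the protocol elsewhere says must not be re-exposed.

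The wording still matters although accrual halts after the safety lead-in, because subjects on treatment continue (sections 5.3 and 12.3). Ipilimumab ends after at most four doses. Nivolumab continues until progression or prohibitive toxicity (section 5.4.2), so the gap matters mainly for nivolumab.

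**Working it through.** The plan gives no figure to reproduce for this point. The check is to apply both sections to the same events, assuming that the rash is judged immune-related and that Grade 3 counts as severe.

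| Event | 6.1.3 nivolumab table | 10.3.6 |
|---|---|---|
| First Grade 3 rash | Withhold; resume at Grade 0 or 1 | Withhold according to severity, give steroids; may resume after taper |
| Second Grade 3 rash | Same row: withhold; resume at Grade 0 or 1; no mention of a second episode | Permanent stop |
| Grade 4 rash | Permanent stop | Permanent stop (if life-threatening) |
| Second episode of a Grade 3 reaction not named in the table | Permanent stop | Permanent stop |

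The two sections part company on the second line only. The other lines show that the table generally follows the 10.3.6 rule, which points to an omission in the named row.

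Other provisions do not close the gap:

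- Section 5.6.1 requires steroids to be tapered before immunotherapy resumes. That governs when to resume, not whether to resume after a recurrence.
- The table's 12-week stop concerns reactions that persist, not reactions that resolve and return.
- Section 6.1 lets investigators be more conservative than the guidelines. That is permission, while 10.3.6 is an obligation.

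Size of the exposed group, from section 5.2: 3 dose levels × up to 6 subjects = at most 18. If the 5 mg level shows no more than 1 DLT in 6, the lead-in ends with 6. No probability of recurrence is calculated, because the documents give no rate.

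**The case against.** The strongest reply is that the 10.3.6 sentence stands under a heading for other immune-mediated events, after separate paragraphs on organ-specific toxicities. The 6.1.3 table has a matching block for other reactions with the same two rules. Read that way, the sections agree. The reading is possible but is not the better one: the paragraph opens with suspected immune-related reactions in general, and the rule applies to any severe one.

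Second, the rash row is silent; it does not authorise re-dosing after a repeat episode. The tables are introduced as recommendations and 10.3.6 is mandatory, so a site complies with both by stopping. This stands, and it is why the point is an inconsistency that can be resolved. A reader might infer a flat contradiction, or a protocol that permits re-dosing after recurrence; the text supports neither.

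Third, section 5.6.1 sends sites to the Appendix 2 algorithms, whose figures are not shown in the text available for review. The skin figure may already address recurrence. The readable footnote there covers only SJS and TEN. This also stands, so nothing here claims that the protocol lacks a recurrence instruction for rash everywhere outside 10.3.6.

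Fourth, weekly safety calls during the lead-in (section 13.1) review significant toxicities and might catch such a case. They are a safeguard, not a dosing rule.

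A reader might also extend the point to other entries, which the documents do not firmly support:

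- **Endocrine rows** ("Grade 2 or 3 hypophysitis" and "Grade 3 hyperglycemia"). They have the same layout, but 10.3.6 describes moderate- to high-grade endocrine cases managed with hormone replacement, so an exemption may be intended.
- **Neurologic line** ("New-onset moderate or severe neurologic signs or symptoms"). This is best read as a hold pending diagnosis; confirmed immune-mediated encephalitis is already a permanent stop.
- **Ipilimumab table.** It has no recurrence stop, but it is headed as covering mild to moderate reactions, although some of its rows are severe. Section 6.1 already says that both drugs are held or stopped together when the guidelines call for it in an immune-related event.

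**Conclusion.** The point holds for recurrent Grade 3 rash: the named row in 6.1.3 and the rule in 10.3.6 lead to different dosing actions, and the table's recurrence stop is labelled in a way that leaves rash out. It is minor. At most 18 subjects are exposed, 10.3.6 describes most skin cases as low or moderate grade, and no endpoint or analysis is affected.

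The conclusion assumes that Grade 3 means severe, that the 10.3.6 rule applies to all immune-related reactions rather than only to those not discussed above it, and that the unseen Appendix 2 skin figure does not already tell sites to stop on recurrence. If that figure does so, what remains is a need to make the 6.1.3 row agree.

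**What to change.** Add one footnote to the 6.1.3 nivolumab table, stated to apply to every row: recurrence of the same Grade 3 (severe) immune-related reaction means permanent discontinuation of nivolumab under 10.3.6, with ipilimumab stopped as well under section 6.1.

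The sponsor should also state whether endocrine events controlled on hormone replacement are exempt, using the same wording in 6.1.3 and 10.3.6, and confirm that the Appendix 2 figures agree.

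The cost is a short wording change and a memo to sites, with no new data, visits or patients. The downside is that an occasional patient stops checkpoint therapy earlier than under the row alone.
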